#### 11.4.2 Definition of analysis endpoints; primary, secondary, tertiary, exploratory, and safety

##### Primary efficacy endpoint

Tumor response in terms of clinical benefit will be assessed by RECIST 1.1 criteria from centrally read CT scans obtained at the 16 week assessment. Tumor response is judged relative to baseline tumor assessments. An evaluable subject will be considered to have a response of CB if the assessment indicates SD, PR, or CR. The primary assessment is among the evaluable subjects in the FAS at 16 weeks. An evaluable subject who does not have a week 16 assessment for any reason remains in the evaluable subset of the FAS and is considered a failure to achieve CB (SD, PR, or CR).

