#### 3.2.2 Secondary Efficacy Outcome Measures

- Response of CB in a subject at 16 weeks, regardless of central confirmation of AR status (FAS)

The following secondary efficacy outcome measures apply to both the evaluable subset of the FAS as well as to the FAS:

- CB response at 24 weeks
- OR at weeks 16 and 24. OR is defined as attainment of a CR or PR at 16 and 24 weeks, respectively, as measured by RECIST 1.1
- BOR as measured by RECIST 1.1 and defined as: the best response recorded from the start of the study treatment until the end of treatment taking into account any requirement for confirmation. For a subject with non-measurable (non-target) disease only at baseline, SD will be defined as those with non-CR/non-PD combined response
- PFS defined as the time elapsed between treatment initiation and tumor progression as measured by RECIST 1.1 or death
- TTP defined as the time elapsed between treatment initiation and tumor progression as measured by RECIST 1.1 or death due to disease progression
- Duration of response (time from documentation of tumor response to disease progression or

Protocol: A Phase 2 Open Label, Multi-Center, Multinational Study Investigating The Efficacy and Safety Of GTx-024 On Advanced, Androgen Receptor-Positive Triple Negative Breast Cancer (AR+ TNBC)	Compound No.: GTx-024 Author: [name]
---	---

death)

- Duration of survival (time from date of first dose of study drug to death or last follow up date with a maximum of 24 months post first dose)

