### 7.3 Treatment Phase

The first dose of study drug will be administered at baseline (Visit 2). GTx-024 will be administered for up to 12 months from the first dose of treatment or until disease progression (whichever is sooner), subject's withdrawal of consent, or intolerability. Subjects who benefit from the treatment at week 16 and still benefit from the treatment at week 24 may continue to receive GTx-024 for a total of 12 months from the date of the first dose of study treatment (as long as they still benefit from the treatment during these 12 months). Subjects who continue to demonstrate a beneficial response at 12 months will be offered to continue in a safety extension study under a separate protocol.

After randomization on Day 1, a safety check involving a comprehensive metabolic panel (Chem 14), including serum calcium and liver function tests, will be performed at Week 2 ( $\pm 3$  days). The Week 2 safety check should include a clinic visit. The investigator may repeat these checks at Week 3 ( $\pm 3$  days) if clinically indicated.

During the first 4 months of the treatment phase, the subjects will be asked to come for a visit every 4 weeks (Visits 3, 4, 5, and 6), and then every 8 weeks (Visit 8 and Visits 10–12 as required if still on treatment). Visits 7 and 9 at weeks 20 and 28 will only take place in subjects who have CR or PR at Visit 6 (week 16) or Visit 8 (week 24), respectively (see below).

The following tests and procedures will be performed during Visits 3, 4, 5, 6, and 8 in the treatment phase:

- Review concomitant medications
- Physical examination, including weight and vital signs (heart rate, respiratory rate, body temperature, blood pressure in a sitting position)
- ECOG performance status
- Blood sampling for: hematology, biochemistry, serum lipid profile, coagulation status, serum hormones, and PSA
- Urine analysis, only if clinically indicated
- Urine pregnancy test for premenopausal subjects (at the site)
- AE collection
- Subjects will be asked to complete a QoL questionnaire
- GTx-024 drug accountability/dispensation

Radiologic assessments for anti-tumor effect will be done every 8 weeks whilst subjects receive treatment (Visit 4, Visit 6, Visit 8, and thereafter). In addition, if a subject has CR or PR at Visit 6 (week 16) or Visit 8 (Week 24), in compliance with RECIST 1.1 guidelines, a confirmation of the CR or PR should be done 4 weeks later (i.e., Visit 7 and/or Visit 9, as

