### 8.1 Clinical Evaluations

All treatment decisions will be based on Investigator assessments, including determination of PD.

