### 11.1 Study Hypotheses

This trial will employ a Simon's two-stage (optimal) design. The assumptions for the design are as follows:

- $H_0$ : CBR  $\leq$  0.05
- $H_1$ : CBR  $\geq$  0.20
- $\alpha$  = 0.05 (one sided)
- Power = 90%

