### 11.2 Sample Size Considerations

Based on the above assumptions, a sample size of N = 41 TNBC subjects with centrally confirmed AR+ status who received at least one dose of study treatment (evaluable subjects) are needed if the trial continues to completion of the second stage. The trial will proceed to the second stage if at least 2 subjects among the first 21 evaluable subjects achieve CB, defined as SD, PR, or CR as per RECIST 1.1. If the trial proceeds to the second stage, a statistical success that favors further evaluation of GTx-024 18 mg in future trials will require at least 5/41 subjects to achieve CB at week 16, i.e., the null hypothesis of an unacceptably low rate of CB,  $\leq$  5.0%, can be rejected in favor of the alternative hypothesis that indicates the higher rate, 20%, is more likely. The lower limit of the exact 90% confidence interval at exactly five CBs, 6.1%, exceeds 5.0%. At any time during the first stage, if two subjects achieve CB at week 16, the trial will proceed to the second stage; otherwise, it will be halted for lack of efficacy. If at any time, 5 subjects achieve CB at week 16, the efficacy criteria has been met; however, the trial should proceed to full accrual of 41 evaluable subjects in order to better characterize the CB rate, evaluate secondary endpoints, and describe the safety profile of the drug.

Subjects whose AR+ status is not centrally confirmed will be replaced in order to accrue the necessary number of evaluable AR+ subjects to be included in the primary analysis. Subjects who are not confirmed AR+ may remain on the trial, but will not be part of the primary efficacy analysis – these subjects will contribute to secondary and tertiary analyses as noted below. This may result in up to 14 additional subjects enrolled (a total of 55 subjects) to account for discordant local/central AR status results and for the rare subject who is enrolled but never received study drug.

Protocol: A Phase 2 Open Label, Multi-Center, Multinational Study Investigating The Efficacy and Safety Of GTx-024 On Advanced, Androgen Receptor-Positive Triple Negative Breast Cancer (AR+ TNBC)	Compound No.: GTx-024 Author: [name]
---	---

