#### 11.4.3.2 Primary efficacy analysis

The primary efficacy analysis is based on rules as set forth in Simon's two-stage (optimal) design as previously described, and is based on the proportion of evaluable subjects in the FAS who achieve CB at 16 weeks. At least 2/21 subjects must achieve CB in order for the trial to proceed to the second stage. If the trial proceeds to the second stage,  $\geq 5/41$  subjects must have CB at 16 weeks to deem the efficacy criteria to have been met. This is the minimum number of successes needed to rule out an unacceptably low, 5%, CB rate (lower limit of the 90% confidence interval). The exact 90% and 95% confidence intervals about the CBR at week 16 will be constructed.

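### Week-16 clinical benefit has no rule for centrally read progression before week 16, so a subject who already has a progression event can still count toward 2/21 and 5/41

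*Combined protocol and SAP*

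**What the plan says.** Section 11.4.2 (Primary efficacy endpoint) takes CB from the central reading of the 16-week assessment under RECIST 1.1. A subject succeeds if that assessment shows SD, PR or CR. On the reference it says: "Tumor response is judged relative to baseline tumor assessments". An evaluable subject with no week-16 assessment is a failure, and Section 11.4.3.7 repeats this. The other definitions of CB (Protocol Summary and Sections 3.1, 3.2.1, 4, 11.2 and 11.4.3.2) add no condition about progression before week 16.

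An earlier scan exists. Section 7.3 states: "Radiologic assessments for anti-tumor effect will be done every 8 weeks whilst subjects receive treatment", so week 8 precedes week 16. The imaging footnote to the Schedule of Events has each study read both locally and centrally, with medical decisions resting on the local read. Section 8.1 agrees: "All treatment decisions will be based on Investigator assessments, including determination of PD". It also sends the scans to the central facility for the final efficacy analysis.

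Section 3.2.2 has "PFS defined as the time elapsed between treatment initiation and tumor progression as measured by RECIST 1.1 or death", and Section 11.4.2 uses objective progression for both PFS and TTP.

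**The concern.** The rule looks at one scan. It asks whether the tumor is stable or better at week 16, not whether the subject has remained free of progression up to week 16. Two situations are left open.

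- **Central progression at week 8, no local progression.** The subject stays on treatment and is scanned at week 16. If that central read is within stable-disease limits of baseline, she meets the stated definition of CB. The missing-scan rule cannot reach her, because the scan exists.
- **Shrinkage followed by regrowth.** The endpoint names RECIST 1.1 and, in the next sentence, names baseline as the reference. Nothing states the reference for progression, so two readers could score the same scan differently.

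Compared with a rule that counts earlier central progression as failure, the omission can only add successes. It acts on both decisions: whether to open stage 2 and whether to declare efficacy. The same subject could also appear in the report as a week-8 progression event and a week-16 success.

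**Working it through.** **1. The plan's own design.** Inputs from Sections 11.1, 11.2 and 11.4.3.2:

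- null rate 5% ("This is the minimum number of successes needed to rule out an unacceptably low, 5%, CB rate")
- alternative 20% ("the alternative hypothesis that indicates the higher rate, 20%, is more likely")
- one-sided alpha 0.05 and power 90%
- stage-1 rule: "At least 2/21 subjects must achieve CB in order for the trial to proceed to the second stage"
- final rule: at least 5 of 41

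Formulas, with p the probability that a subject is counted as CB:

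- P(pass stage 1) = 1 − (1−p)^21 − 21·p·(1−p)^20
- P(success) = Σ over x = 2 to 21 of Bin(x; 21, p) × P(Bin(20, p) ≥ 5 − x)

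At p = 0.05, stage 1 gives 1 − 0.3406 − 0.3764 = 0.283, and P(success) = 0.0457. At p = 0.20, P(success) = 0.9017. A grid search for the Simon optimal design returns the same 21/41 with cut-offs 2 and 5. The sample size is therefore correct for the stated assumptions, and the issue is only what counts as a success.

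**2. Following one subject through the rules (week 8 central PD, local SD).**

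| Step | Section | Result |
|---|---|---|
| Treatment decision at week 8 | 8.1, Schedule of Events | Local read governs; stays on drug |
| Week-16 scan | 7.3 | Taken |
| Missing-scan failure rule | 11.4.2, 11.4.3.7 | Does not apply |
| Week-16 central read SD against baseline | 11.4.2 | Counted as CB |
| PFS and TTP | 11.4.2 | Event at week 8, if the central read governs, as 8.1 indicates |

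**3. Regrowth, with hypothetical target sums of 100 (baseline), 60 (week 8) and 85 (week 16).** Against baseline: 85/100 − 1 = −15%. Against the smallest sum: 85/60 − 1 = +42%. The protocol does not reproduce the RECIST 1.1 rule. If, as I assume, those criteria measure progression from the smallest sum on study, the baseline sentence and the named criteria disagree about this scan.

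**4. Size, as illustration.** Let the true progression-free CB rate be 5%, and let a share m of evaluable subjects be counted as CB despite earlier central progression, so p = 0.05 + m. The documents give no value for m; the values below are assumptions.

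| m | P(pass stage 1) | P(success) |
|---|---|---|
| 0 | 0.283 | 0.046 |
| 1 point | 0.362 | 0.085 |
| 2 points | 0.438 | 0.138 |

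**5. One misclassified subject, the rest at 5%.** One subject in 41 is 2.4 percentage points.

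- If she is among the first 21, one success among the other 20 is enough: 1 − 0.95^20 = 0.642, against 0.283. P(success) becomes 0.132.
- If she is in stage 2, P(success) becomes 0.109.

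**The case against.** **RECIST 1.1 is named, and the text does not say baseline only.** A central reader applying the criteria in full might score the regrowth example as progression, or carry week-8 progression forward. This stands as far as it goes: a reader might infer that regrowth is certainly counted as benefit, and the documents do not support that. They leave a conflict between one sentence and the criteria named beside it.

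**Most progressors already fail.** Section 7.3 stops treatment at progression and ties imaging to treatment, so a local progressor at week 8 will usually have no week-16 scan. This stands. Section 5.4.4 does ask withdrawn subjects to continue scheduled evaluations, but that is a weak extra route. For the discordant-read case, a persisting new lesion would still be progression at week 16. What remains is reversals and reading differences.

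**The size is assumed.** Three or 5 points would give 20.3% or 35.3%, and a reader might infer a false-positive risk of that order. Nothing in the documents supports it: 5 points on a true 5% would mean that half of all apparent successes were misclassified.

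**The hypothesis concerns CB as defined.** For that quantity the error is 4.6%. Inflation appears only if 5% is meant as a progression-free rate, and the documents do not say how it was derived. This stands as a condition on the figures.

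**Detail is deferred to a separate SAP (Section 11).** That text is not in the material reviewed, so a clause there cannot be excluded. The rule still belongs in the protocol, because it determines the stage-1 decision.

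**Conclusion.** The gap is real but narrow. As written, Section 11.4.2 allows a subject with centrally read progression at week 8 and no local progression to count toward 2/21 and 5/41 if her week-16 central read is within stable-disease limits of baseline. It also leaves the reference for progression ambiguous after shrinkage. Nothing in the supplied text closes either point.

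The number of such subjects is probably small and is not given. The figures of 8.5% and 13.8%, against 4.6%, illustrate sensitivity and do not estimate the trial's error rate. They rest on an assumed 1 or 2 points of misclassification and on reading the 5% null as a progression-free rate. What does not depend on that assumed rate is that, with cut-offs of 2 and 5, one subject can decide either stage. The change is worth making because it settles a decision rule, not because large inflation has been shown. The sample size needs no revision.

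**What to change.** In Section 11.4.2, replace the baseline sentence with wording to this effect: *The week-16 response is the central RECIST 1.1 time-point response, with progression judged against the RECIST 1.1 reference and not against baseline alone. A subject with centrally read PD at any assessment up to and including week 16 is counted as not having CB.*

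Apply the same rule to CBR at week 24 and to the stage-1 count, align Section 3.2.1, and carry it into the SAP.

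The cost is a few sentences. The week-8 scans are already scheduled and centrally read, so no visit, scan or subject is added. How treatment decisions are made is not affected. The downside is that the observed CBR may be slightly lower.

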##### Secondary efficacy endpoints

- CBR in the FAS at 16 weeks.

The following secondary efficacy endpoints will be assessed among evaluable subjects (if not already listed above), the FAS (if not already listed above), and the PPS:

Protocol: A Phase 2 Open Label, Multi-Center, Multinational Study Investigating The Efficacy and Safety Of GTx-024 On Advanced, Androgen Receptor-Positive Triple Negative Breast Cancer (AR+ TNBC)	Compound No.: GTx-024 Author: [name]
---	---

- CBR at weeks 16 and 24
- ORR (PR or CR assessed by RECIST 1.1 criteria) at weeks 16 and 24.
- Best (confirmed) overall response rate (BOR). BOR is defined as the best observed response for each subject up to and including the EOT. Responses of PR or CR should be confirmed by a repeat assessment at least 4 weeks later.
- PFS: PFS is defined as the time from treatment initiation until objective tumor progression or death. Subjects who have no PFS events will be censored at the date of the last adequate tumor assessment. If the subject has no post-baseline tumor assessments, they will be censored at the time of enrollment.
- TTP: TTP is defined as the time from treatment initiation until objective tumor progression or death due to PD. Subjects who have not progressed will be censored at the date of the last adequate tumor assessment. If the subject has no post-baseline tumor assessments but was known to be alive, they will be censored at the time of enrollment.
- Duration of response: Duration of response, in responders, is defined as the period from the date of initial PR or CR until the date of PD or death from any cause. Only subjects with BOR of CR or PR (i.e., responders) will be included in the analysis of duration of response. Subjects with no documented progression or death after CR or PR will be censored at the last date at which they are known to have had the CR or PR.
- Overall Survival: OS is defined as the time from treatment initiation until death or date of last follow up to a maximum of 24 months post treatment initiation. Subjects known to be alive at their last follow up will be censored at that time.

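### The PFS rule for subjects with no scan after baseline does not exclude those who have died; applied literally, it censors early deaths at time zero and raises the PFS curve

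*Combined protocol and SAP*

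**What the plan says.** All the relevant wording is in Section 11.4.2, under the secondary efficacy endpoints.

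- **PFS, event and clock:** "PFS is defined as the time from treatment initiation until objective tumor progression or death". Section 3.2.2 likewise makes death an event.
- **PFS, general censoring:** "Subjects who have no PFS events will be censored at the date of the last adequate tumor assessment".
- **PFS, no scan after baseline:** "If the subject has no post-baseline tumor assessments, they will be censored at the time of enrollment".
- **TTP, no scan after baseline:** "If the subject has no post-baseline tumor assessments but was known to be alive, they will be censored at the time of enrollment".

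Section 11.4.3.3 estimates PFS by Kaplan-Meier, as a median and as survival at key time points, in the evaluable subjects, the FAS and the PPS. Under Section 7.3 the first scheduled scan on treatment is at week 8 (Visit 4).

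**The concern.** The two no-scan sentences differ in one condition. TTP, where only deaths due to progression count, restricts day-zero censoring to living subjects. PFS, where every death counts, does not. A programmer who compares the two could take the difference as intended and censor at time zero every subject without a scan, including those who died.

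On that reading the two endpoints no longer fit together. A death due to progression before week 8 would be a TTP event but a PFS censoring. Every TTP event should also be a PFS event, yet the PFS curve could then lie above the TTP curve. The subjects removed would be those with the worst outcomes, so the error would always favour the drug.

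There is also a smaller mismatch: the PFS clock starts at treatment initiation, while the censoring date is enrollment, which need not be the same day.

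**Working it through.** The documents give no figure for PFS, so there is nothing of the plan's own to reproduce. The check is how far the two readings differ.

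**Inputs from the protocol:** progression or death as the event (11.4.2); Kaplan-Meier (11.4.3.3); first scheduled scan at week 8 (7.3); 41 evaluable subjects at full accrual (11.2).

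**Assumptions, not in the documents:** d, the share of subjects who die without any scan after baseline, from 2.5% to 20% (about 1 to 8 of 41); PFS at 16 weeks of 20% or 30% with early deaths counted; an exponential median of 3 months.

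**Formula.** Let n subjects be at risk on day 1, with nobody else censored before the first scan.

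- Early deaths as events: the curve stands at 1 - d once those deaths have occurred.
- Early deaths censored at time zero: they enter no risk set, and the curve is still at 1.
- From then on the risk sets are identical, so S_literal(t) = S(t) / (1 - d) at and after the first scan.

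For the exponential median m, S_literal reaches 0.5 when S = 0.5(1 - d), so m_literal = m × [-ln(0.5(1 - d))] / ln 2. With m = 3 and d = 10% this is 3 × 0.799 / 0.693 = 3.46 months.

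| d | 1/(1 - d) | 20% reads | 30% reads | 3-month median reads |
|---|---|---|---|---|
| 2.5% | 1.026 | 20.5% | 30.8% | 3.1 |
| 5% | 1.053 | 21.1% | 31.6% | 3.2 |
| 10% | 1.111 | 22.2% | 33.3% | 3.5 |
| 15% | 1.176 | 23.5% | 35.3% | 3.7 |
| 20% | 1.250 | 25.0% | 37.5% | 4.0 |

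**Constructed example, 41 subjects.** Four die before week 8 without a scan, 15 progress at week 8, 11 at week 16 and 6 at week 24; 5 are censored at week 24.

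- Week 8: (41 - 4 - 15)/41 = 22/41 = 53.7% with the deaths as events; 22/37 = 59.5% with them censored at time zero.
- Week 16: (22 - 11)/41 = 11/41 = 26.8%, against 11/37 = 29.7%.
- The ratio in each case is 41/37 = 1.108 = 1/(1 - 4/41), as the formula requires.
- The estimated median is week 16 on both readings, because both curves first fall below 50% at that scan.

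**The case against.** **The sentence has a harmless reading.** The general rule just before it covers only subjects with no PFS event. The no-scan sentence can be read as giving the date for those among them who were never scanned, and a subject who died is not one of them. The contrast with TTP can also be explained: TTP's general rule covers subjects who have not progressed, which does not by itself exclude someone who died of progression unscanned, so TTP needs the extra condition and PFS may not. This stands. A reader might infer that the plan definitely censors early deaths; the text does not establish that. It permits that reading without requiring it.

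**Early unscanned deaths may be few.** Eligibility requires ECOG 0 or 1 and excludes a life expectancy under 4 months, and the end-of-treatment and early-termination visits include imaging. This also stands, and makes the lower rows of the table less plausible, but it does not make d zero.

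**The consequence is limited.** PFS has no hypothesis test. The stage 1 and final decisions rest on week 16 clinical benefit, where a missing assessment is a failure. The PPS requires a completed week 16 evaluation, so these deaths are not in it. All correct; the effect is confined to PFS in the evaluable subjects and the FAS.

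**A separate SAP may settle it.** Section 11 announces one for missing data and time-to-event imputation, but it is not part of the document reviewed. The imputation it describes concerns the gap between the last event-free time and the first event date, which does not clearly cover whether a known death counts.

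**A reader might infer that the duration-of-response rule is biased upward as well**, since an event-free responder is "censored at the last date at which they are known to have had the CR or PR" rather than at the last adequate assessment. The documents do not support this. Duration "is defined as the period from the date of initial PR or CR until the date of PD or death from any cause", so a responder who falls back to stable disease and later progresses or dies is still an event. Only responders with neither are moved to an earlier date. Each Kaplan-Meier factor, 1 - events/at risk, then keeps its events with an equal or smaller number at risk, so the curve can only stay the same or fall. A simulation with an assumed 24-week median, 8-weekly scans and follow-up uniform over 8 to 48 weeks agrees. Against a true 24-week value of 0.50, censoring at the last scan gives 0.497; moving every event-free responder back one scan gives 0.399.

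**Conclusion.** The point holds as an ambiguity with one harmful reading. Applied literally, the PFS no-scan sentence contradicts the PFS definition and inflates the curve after the first scan by 1/(1 - d): about 3% relative at d = 2.5% and 11% at d = 10%. Both values of d are assumptions, and the formula takes nobody else as censored before the first scan. If no subject dies unscanned, the two readings agree.

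The wording should still be corrected, because a stated censoring rule that can be programmed in two ways can give a wrong published estimate, and on the harmful reading the error is always upward. The primary endpoint and the two-stage decision rule are unaffected. The duration-of-response rule is not a second instance of the problem: relative to censoring at the last adequate tumor assessment, it can only lower the estimate or leave it unchanged.

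**What to change.** Replace the PFS no-scan sentence in Section 11.4.2, and carry the same text into the SAP:

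> *A subject without any tumor assessment after baseline who has not died is censored at day 1 (treatment initiation); a death before the first assessment is a PFS event on the date of death.*

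This matches the PFS definition, restores agreement with TTP and puts the censoring date on the same clock as the endpoint. It needs no new data: vital status is already followed in all subjects (Section 7.5), and OS already requires dates of death. The cost is one clause and, if early deaths occur, a slightly lower reported PFS than the literal rule would give.

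Optionally, for consistency only, duration of response could be censored at the last adequate tumor assessment, as PFS is. That would leave the estimate unchanged or raise it, so it should not be presented as removing an upward bias.
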